from medical history if not older than 12 months and one during screening period) with both measurements of ALT or AST are  $\leq 2 \times \text{ULN}$

- b. Normal or clinically not relevant levels of ALP ( $\leq 1.5 \text{ ULN}$ )
  - c. Has total bilirubin (TBL)  $\leq 22.2 \mu\text{mol/L}$ , which corresponds to  $\leq 1.3 \text{ mg/dL}$
  - d. Has conjugated (direct) bilirubin of  $\leq 0.3 \text{ mg/dL}$  (i.e.  $5.1 \mu\text{mol/L}$ )
  - e. Has normal or clinically not relevant levels of GGT ( $\leq 2.0 \text{ ULN}$ )
  - f. International normalized ratio  $\leq 1.2 \times \text{ULN}$ , unless on anticoagulant therapy
  - g. Platelet count  $\geq 100 \text{ G/L}$
  - h. Has albumin  $\geq 3.5 \text{ g/dL}$ .
7. Is not of childbearing potential or, if of childbearing potential, is not pregnant as confirmed by a negative serum human chorionic gonadotropin test at screening and is not planning a pregnancy during the course of the study.
8. Women of childbearing potential (WOCBP) and male patients with WOCBP partners must agree to use a dual method of contraception as defined in the study protocol or practice complete abstinence from sexual intercourse if this is the patient's usual and preferred lifestyle throughout the duration of the study and for 90 days after stopping study drug. Patients who are using hormonal contraceptives should be instructed to use an additional contraceptive measure during the study. Note: A woman is considered of childbearing potential following menarche and until becoming postmenopausal unless permanently sterile. A postmenopausal state is defined as no menses for  $>12$  consecutive months without an alternative medical cause.  
A follicle-stimulating hormone level in the postmenopausal range will be used to confirm a postmenopausal state in women  $<55$  years of age. Permanent sterilization methods include hysterectomy, bilateral salpingectomy, and bilateral oophorectomy.

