### 8.3. Drug-Induced Liver Injury

#### 8.3.1. Normal values at baseline

Drug-induced liver injury (DILI) monitoring in patients with **normal liver transaminases and bilirubin at baseline** should be performed throughout the study according to the procedures summarized below:

- If patients with normal baseline liver indices develop elevations of aspartate aminotransferase (AST) or alanine aminotransferase (ALT) >2 upper limit of normal (ULN) or total bilirubin (TBL) >1.5 ULN values during the study, repeat testing should be performed within 48 hours.
- If there are persistent elevations (ALT or AST >2 ULN or TBL >1.5 ULN) upon repeat testing, close observation (testing and physical examination 2 to 3 times per week) should be implemented. An important purpose of the close observation is to gather additional clinical information to seek other possible causes of the observed liver test abnormalities, such as 1 of the following: acute viral hepatitis, alcoholic and autoimmune hepatitis, hepatobiliary disorders, cardiovascular causes, or concomitant treatments. Discontinuation of study drug should be considered.

[figure not shown]
Study drug should be discontinued, and the patient should be followed until resolution of signs or symptoms, in the following situations:

- ALT or AST >8 ULN.
- ALT or AST >5 ULN for more than 2 weeks.
- ALT or AST >3 ULN and (TBL >2 ULN or international normalized ratio [INR] >1.5).
- ALT or AST >3 ULN with the appearance of fatigue, nausea, vomiting, right upper quadrant pain or tenderness, fever, rash, and/or eosinophilia (>5%).

For any patients who present with a constellation of syndromes indicative of liver disease as per the Investigator's overall assessment (i.e., fatigue, nausea, vomiting, right upper quadrant pain or tenderness, fever, rash, and/or eosinophilia [>5%]), perform liver function tests to determine if liver disease is worsening.

Re-initiation of study drug may be considered after consultation with the Medical Monitor.

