### 8.3.2. Elevated values at baseline

Drug-induced liver injury (DILI) monitoring in patients with **elevations in liver transaminases or bilirubin at baseline** should be performed throughout the study according to the procedures summarized below:

- If patients with abnormal baseline liver indices develop elevations of AST or ALT  $>2$  baseline average or TBL  $>1.5$  baseline average values during the study, repeat testing should be performed within 48 hours.
- If there are persistent elevations (ALT or AST  $>2$  baseline average or TBL  $>1.5$  baseline average values) upon repeat testing, then close observation (testing and physical examination 2 to 3 times per week) should be implemented and discontinuation of study drug should be considered.

[figure not shown]
Study drug should be discontinued, and the patient should be followed until resolution of signs or symptoms, in the following situations:

- Baseline average measurements were  $<2 \times$  ULN and ALT or AST increases to  $>5 \times$  baseline measurements.
- ALT or AST increase  $>2 \times$  baseline average measurements AND the increase is accompanied by a concomitant increase in TBL to  $>2 \times$  baseline average measurements or the INR concomitantly increases by  $>0.2$ .

For any patients who present with a constellation of syndromes indicative of liver disease as per the Investigator's overall assessment (i.e., fatigue, nausea, vomiting, right upper quadrant pain or tenderness, fever, rash, and/or eosinophilia [ $>5\%$ ]), perform liver function tests to determine if liver disease is worsening.

Re-initiation of study drug may be considered after consultation with the Medical Monitor.

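### Protocol 8.3.2 (text only; Figure 9 not available): the ALT/AST-alone stop lapses once the baseline average reaches 2.0 × ULN, exceeds 8.3.1's 8 × ULN limit for baselines between 1.6 and 2.0, and comes with no time-limited stop

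*Protocol*

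**What the plan says.** Protocol 8.3.1 covers patients with normal liver values at baseline and lists four situations in which study drug should be discontinued. Three are numeric: "ALT or AST >8 ULN"; "ALT or AST >5 ULN for more than 2 weeks"; and "ALT or AST >3 ULN and (TBL >2 ULN or international normalized ratio [INR] >1.5". The fourth is ALT/AST above 3 × ULN with symptoms.

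Protocol 8.3.2 covers patients with "elevations in liver transaminases or bilirubin at baseline" and lists two such situations. The first, on ALT/AST alone, is "Baseline average measurements were $<2 \times$ ULN and ALT or AST increases to $>5 \times$ baseline measurements". The second is ALT/AST above 2 × baseline average "AND the increase is accompanied by a concomitant increase in TBL to" more than 2 × baseline average, or with an INR rise above 0.2. For elevations that persist on retest, close observation "should be implemented and discontinuation of study drug should be considered".

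On entry values, inclusion 6a uses two measurements, one of which may come "from medical history if not older than 12 months and one during screening period) with both measurements of ALT or AST are" no higher than 2 × ULN. Exclusion 5 removes only a confirmed value above 2 × ULN. Exclusion 8, citing exclusion 5, writes the limit as below 2 × ULN.

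8.3.2 does not define its baseline average. SAP 3.2 defines baseline for ALT, AST, ALP and total bilirubin as the mean of screening and Day 1 pre-dose. Protocol 11.1 uses the last value before the first dose.

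**The concern.** In the 8.3.2 stops, ULN appears only as a condition on the baseline, never as a limit on treatment. This has three consequences.

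- **Boundary.** A patient whose baseline average is 2.0 × ULN or more fails the condition, so the ALT-alone stop does not apply.
- **Ceiling.** Near the top of the eligible range, 5 × baseline lies above the 8 × ULN at which a normal-baseline patient must stop.
- **Duration.** No rule limits how long ALT/AST may stay above 5 × ULN while below 5 × baseline.

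In these ranges, continued dosing depends on judgement at about 14 sites. The gap also affects oversight. Protocol 4.6 rule #4 imports the 8.3 criteria, and two patients meeting it trigger suspension and DSMC review. A patient in the gap does not count under #4.

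**Working it through.** **Inputs.** Limits are from Protocol 8.3.1 and 8.3.2, eligibility from 4.2 (6a) and 4.3 (exclusions 5 and 8), and the baseline definition from SAP 3.2. Let B be baseline ALT/AST in multiples of ULN.

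**1. Single-value stop.** 8.3.2 stops above 5B for B < 2.0. It equals 8.3.1's limit when 5B = 8, so B = 8/5 = 1.6. The largest excess is just under 10 × ULN: at B = 1.99, 9.95/8 − 1 = 24.4%.

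**2. Range with no time limit.** Width = max(0, 5B − 5), in multiples of ULN.

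| B | Stop now (× ULN) | Against 8 × ULN | Width above 5 × ULN with no time limit | Lower of 5B and 8 |
|---|---|---|---|---|
| 0.8 (bilirubin raised only) | >4.0 | tighter | 0 | >4.0 |
| 1.05 | >5.25 | tighter | 0.25 | >5.25 |
| 1.2 | >6.0 | tighter | 1.0 | >6.0 |
| 1.4 | >7.0 | tighter | 2.0 | >7.0 |
| 1.6 | >8.0 | equal | 3.0 | >8.0 |
| 1.8 | >9.0 | looser | 4.0 | >8.0 |
| 1.99 | >9.95 | looser | 4.95 | >8.0 |
| 2.0 | none | none | no upper bound | >8.0 |

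Patients in 8.3.2 through bilirubin alone are unaffected: with B ≤ 1.0, 5B is at most 5 × ULN.

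**3. Reaching an average of 2.0.** With the 6a pair, both values must be exactly 2.0. With the SAP mean and a screening value s ≤ 2.0, it is enough that the Day 1 value is at least 4 − s. For example, s = 1.9 with Day 1 at 2.2 gives (1.9 + 2.2)/2 = 2.05. Exclusion 5 needs two assessments at least 3 days apart, so a single Day 1 value above 2 × ULN does not exclude the patient.

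**4. Combined stop.** Its ALT limb is 2B against 3 in 8.3.1: tighter below B = 1.5, looser above (4.0 at B = 2.0). Its INR limb is tighter when baseline INR is below 1.5 − 0.2 = 1.3, and its bilirubin limb when baseline bilirubin is below ULN.

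**5. How many patients.** The documents give no baseline ALT distribution. Assume 10%, 20% or 40% enter above ULN: 4.9, 9.8 or 19.6 of 49. SAP 15 records that enrolment was suspended after about 25 randomisations; of 25 the figures are 2.5, 5.0 or 10.0. Reported Grade 3–4 ALT/AST rises are 4/73 = 5.5% (Protocol 1.4.3) or 5/73 = 6.8% (count from 1.4.3.3) in CHB patients over 4 weeks, and 2/24 = 8.3% in NASH subjects on tablets or placebo (5.4). Taking these as a stand-in for a rise above 5 × ULN (an assumption; the documents give no ULN multiple for the grades):

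- of 49: 4.9 × 0.055 = 0.27 to 19.6 × 0.083 = 1.63
- of 25: 2.5 × 0.055 = 0.14 to 10.0 × 0.083 = 0.83

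Restricting to the active arm (37/49 = 0.755) gives 0.27 × 0.755 = 0.20 to 1.63 × 0.755 = 1.23 of 49, before removing rises too brief for a two-week rule to matter.

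For the ceiling, if 5%, 10% or 20% enter above 1.6 × ULN (assumption), that is 2.45, 4.9 or 9.8 of 49. The documents give no rate for exceeding 8 × ULN.

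**The case against.** **Figure 9.** It is the algorithm for exactly these patients and could not be read. It may contain the missing branches. This stands: the point concerns the text, and any correction must start with the figure.

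**A baseline multiple is a legitimate design.** At B = 1.2 it stops any single value above 6 × ULN, where 8.3.1 would allow 6 to 8 × ULN for 2 weeks. The combined stop is often tighter too. This stands below 1.6. It does not explain a looser limit above 1.6, or why the rule lapses at 2.0.

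**Other rules act.** 8.3.2 requires a retest within 48 hours and, if the rise persists, checks 2 to 3 times weekly. Protocol 4.6 rules #1, #2, #5 and #7 require stopping once the investigator judges the event related or, for #7, clinically significant and probably related. More than 2 patients with Grade 3 toxicity in the same category pauses the study. This is real cover, but none of it is a fixed ALT/AST limit for the individual. Protocol 5.4 reports that investigators in the NASH study did not consider its ALT/AST elevations, including two Grade 3 cases, clinically significant. That was another population, but it shows that #7 may not be triggered.

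**The 2.0 boundary is an edge case.** On the 6a pair it is, and exclusion 8 reads as below 2. On the SAP mean it is wider than the single value 2.0, though still uncommon.

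**The counts are inflated.** Agreed: they include brief rises (5.4 calls the two NASH cases transient) and placebo patients, and the CHB rates come from a mostly treatment-naive population.

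**A two-week limit for raised baselines is a clinical choice** in a disease with expected flares. This stands, and the fix treats it as such.

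**Conclusion.** The point holds for the text of 8.3.2 and is worth fixing. The ALT-alone stop disappears at a baseline average of 2.0 × ULN or more, is looser than 8.3.1 above 1.6 and below 2.0 (by less than 25%), and has no duration counterpart at any ALT/AST baseline above ULN.

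A reader might infer more than this:

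- *That raised-baseline patients have no ceiling, or that 8.3.2 is laxer throughout.* Neither is so. Below a baseline of 2.0 the stop is always under 10 × ULN, below 1.6 it is tighter than 8 × ULN, and the combined stop is often tighter.
- *That nothing obliges the investigator to stop.* Protocol 4.6 does, once the required judgement is made. What is missing is a numeric trigger.
- *That the plan as a whole lacks these limits.* That cannot be concluded without Figure 9.

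The likely number affected is small. The 0.3 to 1.6 of 49 (0.1 to 0.8 of 25) rests on an assumed share entering above ULN and on Grade 3–4 rates used as a stand-in. It is an upper-end figure because it counts brief rises and placebo patients. It is not a strict bound: the CHB rates cover 4 weeks and this trial doses for 16. The case for acting is the consequence for such a patient, continued dosing through a marked rise, set against a change of wording.

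**What to change.** Check Figure 9 first. If it already has these branches, align the text of 8.3.2 with it. If not:

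1. Delete the <2 × ULN condition and stop at the lower of >5 × baseline or >8 × ULN. This closes the gap at 2.0 and applies the ceiling already used for normal-baseline patients. By itself it limits the range with no time limit to 8 − 5 = 3 × ULN.
2. Define the baseline average for both 8.3.2 stops as in SAP 3.2, the mean of screening and Day 1 pre-dose. This covers ALT, AST and total bilirubin. The inclusion 6a pair is unsuitable: it omits bilirubin, and one value may be up to 12 months old.
3. Ask the sponsor's hepatology adviser whether to carry over the stop for more than 2 weeks above 5 × ULN. At a baseline of 2.0 that limit is 5/2.0 = 2.5 × baseline, still above the 2 × baseline retest trigger. If adopted, keep testing at least weekly while the two weeks run, because 8.3.3 lets it fall to weekly or less once values stabilise.

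Cost: wording in 8.3.2 (and Figure 9 if it lacks the branches) and one definition. Items 1 and 2 need no new tests; item 3 needs only the weekly minimum. The downside is that a few raised-baseline patients with transient flares stop earlier. Re-initiation after consulting the Medical Monitor, already allowed in 8.3.2, remains open.

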## **Figure 9      Elevated liver transaminase and bilirubin at baseline**

ALT: alanine aminotransferase; AST: aspartate aminotransferase; INR: international normalized ratio; TBL: total bilirubin; ULN: upper limit of normal.

### 8.3.3. General Considerations

For all patients, close observation for suspected drug-induced liver injury includes the following:

- Repeating liver enzyme (ALT, AST, and alkaline phosphatase) and serum bilirubin tests 2 or 3 times weekly.
- The frequency of repeat testing can decrease to once a week or less if abnormalities stabilize or the study drug has been discontinued and the patient is asymptomatic.
- Obtaining a more detailed history of symptoms and prior or concurrent diseases.
- Obtaining a history of concomitant drug use (including non-prescription medications and herbal and dietary supplement preparations), alcohol use, recreational drug use, and special diets.
- Ruling out acute viral hepatitis types A, B, C, D, and E; autoimmune or alcoholic hepatitis; non-alcoholic steatohepatitis; hypoxic/ischemic hepatopathy; and biliary tract disease.
- Obtaining a history of exposure to environmental chemical agents.
- Obtaining additional tests to evaluate liver function, as appropriate (e.g. INR, direct bilirubin).
- Considering gastroenterology or hepatology consultations.

#### **8.4. Pruritus Assessment**

Pruritus will be assessed using a visual analog scale and a 5-D (degree, duration direction, disability, and distribution) itch scale (Refer [Section 19.2](#), [Appendix B](#)) at each study visit after screening.

#### **8.5. Pregnancy**

Pregnancy testing must be performed in all WOCBP as specified in the Schedule of Assessments table, and the results of all pregnancy tests (positive or negative) are to be recorded on the eCRF. If the pregnancy test is positive, the patient will be immediately discontinued from study treatment.

In addition, all WOCBP should be instructed to contact the Investigator immediately if they suspect they might be pregnant (e.g. missed or late menstrual period) at any time during the study. Male patients should contact the Investigator immediately if they suspect they may have fathered a child during the study. When possible, partner's pregnancies should be followed (to term) to determine the outcome.

If a patient becomes pregnant while enrolled in the trial, a Pregnancy Form should be completed and sent to the Sponsor Safety Representative expeditiously, irrespective of whether or not it meets the criteria for expedited reporting. Abortions (spontaneous, accidental, or therapeutic) must also be reported to the Sponsor Safety Representative. Congenital anomalies/birth defects always meet SAE criteria, and should therefore be expeditiously reported as an SAE, using the previously described process for SAE reporting. A Pregnancy Form should also have been previously completed and will need to

be updated to reflect the outcome of the pregnancy. The Investigator must report any pregnancy (including the pregnancy of a male patient's partner), even if no AE has occurred, on a Pregnancy Report Form within 24 hours of the Investigator becoming aware of the pregnancy.

## 9. PK and PD Methods

### 9.1. Pharmacokinetics

EYP001a PK parameters to be determined include:

- Plasma concentration of EYP001a or any relevant active metabolites (as identified in an ongoing phase 1 study).

Fasting plasma samples will be collected at all study visits pre-dose in the morning on Day 1 and at Weeks 2, 4, 6, 8, 10, 12, 14 and 16 and in the morning at the ET Visit.

If by error patient has taken study medication on study Visit days prior to coming to the clinic the accurate time of last dosing and blood draw will be recorded.

Plasma will be stored at -80°C until analysis. Plasma samples will be analysed for EYP001a and any active metabolites using a validated liquid chromatography/mass spectrometry (LC-MS/MS) method.

### 9.2. Pharmacodynamics

EYP001a PD parameters to be determined include:

- Plasma C4 (7 $\alpha$ -hydroxy-4-cholesten-3-one)
- FGF19
- Plasma primary and secondary BAs

Plasma C4, FGF19; BAs (total, primary, and secondary BAs (such as chenodeoxycholic acid [CDCA], deoxycholic acid [DCA], lithocholic acid, and/or others as appropriate) sampling will occur pre-dose paired with PK sampling at all visits during treatment period. A sample will also be collected at the Weeks 28 and 40 (EoS) or ET Visits.

Samples for BAs will be collected and stored centrally frozen for subsequent assessment after the EoS pending ongoing BA profiling related to EYP001a pharmacology.

## 10. Data Quality Assurance

The study may be audited by the Quality Assurance Department at CRO to assess adherence to the clinical study protocol and Quality System. During the conduct of the study, process related audits may be performed. An audit certificate will be provided in the appendices of the final CSR outlining any audits and other related activities performed.

The clinical research site will be monitored by the study monitor to ensure correct performance of the study procedures and assure that the study will be conducted according to the relevant regulatory requirements.

The eCRF entries will be verified with the source documentation.

The study monitor identifies any data to be recorded directly on the eCRF (i.e., no prior

written or electronic record of data), and to be considered to be source data.

Regulatory authorities, the IRB/IEC and/or the Sponsor's clinical quality assurance group may request access to all source documents, eCRFs, and other study documentation for on-site audit or inspection. Direct access to these documents must be guaranteed by the Investigator, who must provide support at all times for these activities.

Quality control principles will be applied throughout the performance of this study. Review procedures will be followed by the CRO for all documents that are generated in relation with the study. Essential study activities of personnel will be checked by other CRO colleagues during execution, and each of them will sign off the documentation for execution or checking of the activities.

An explanation will be given for all missing, unused and spurious data in the relevant sections of the CSR.

## **11. Statistical Methods and Determination of Sample Size**

### **11.1. Statistical Analysis Plan and General Statistical Methods**

All data will be handled and processed according to the sponsor's representative (Novotech [Australia] Pty Ltd) SOPs, which are written based on the principles of GCP.

A Statistical Analysis Plan (SAP) containing the detailed planned statistical methods will be finalized prior to locking of the study database for the interim and final analysis and will form the basis for the programming of the displays and analyses of the final study data. All statistical calculations will be performed using SAS® (SAS Institute Inc., Cary, NC, USA) or similar software.

The statistical analyses will consist of both inferential and descriptive statistics. In general, the data will be presented by dose group. All collected and derived data will be included in the patient data listings.

All inferential analyses will be conducted at a one-sided 0.05 level of significance. Unless otherwise specified, all inferential testing will be one-sided in nature.

Continuous data, other than PK data, will be summarized by treatment group and time point using the number of observations, arithmetic mean, standard deviation, median, minimum and maximum. The coefficient of variance, geometric means and geometric coefficient of variance will also be presented for the concentration-related PK data. Categorical data will be summarized by the number and percentage of patients in each category. Unless specifically stated otherwise, the number of patients in the treatment group (for the specific analysis set) will be used as the denominator for all percentage calculations.

Baseline is defined as the last available non-missing value collected prior to the first administration of IP.

Change from baseline values will be calculated as the difference between the result at a specific time point, and the baseline value for the specific endpoint.

Missing, unused, or spurious data will be handling in the following manner:

- There will be no imputations or substitution made for missing safety data points.
- For the PK analyses, imputations will be made for missing data points.

## **11.2. Definition of Analysis Sets**

The following analysis sets are defined for this study.

### **11.2.1. Intention-To-Treat (ITT) Set**

The ITT set will include all randomized patients, irrespective of whether a patient receives any study drug. This set will be based on randomized treatment. The ITT set will be used for the baseline, demographic summaries and efficacy summaries.

